9.2. Reporting Period

For each patient, the safety event reporting period begins at the time of the patient's first dose of PRISTIQ®, and lasts through the end of the observation period of the study, which must include at least 28 days following the last administration of a drug under study; a report must be submitted to Pfizer Safety (or its designated representative) for any of the types of safety events listed in the table above occurring during this period. If a patient was administered a drug under study on the last day of the observation period, then the reporting period should be extended for 28 days following the end of observation.

Most often, the date of data privacy statement is the same as the date of enrollment. In some situations, there may be a lag between the dates of data privacy statement and enrollment. In these instances, if a patient provides data privacy statement but is never enrolled in the study (e.g., patient changes his/her mind about participation), the reporting period ends on the date of the decision to not enroll the patient.

If the investigator becomes aware of a SAE occurring at any time after completion of the study and s/he considers the SAE to be related to PRISTIQ®, the SAE also must be reported to Pfizer Safety.

9.3. Causality Assessment

The investigator is required to assess and record the causal relationship. For all AEs, sufficient information should be obtained by the investigator to determine the causality of each adverse event. For AEs with a causal relationship to PRISTIQ®, follow-up by the investigator is required until the event and/or its sequelae resolve or stabilize at a level acceptable to the investigator, and Pfizer concurs with that assessment.

An investigator's causality assessment is the determination of whether there exists a reasonable possibility that PRISTIQ® caused or contributed to an adverse event. If the investigator's final determination of causality is "unknown" and s/he cannot determine whether PRISTIQ® caused the event, the safety event must be reported within 24 hours.

If the investigator cannot determine the etiology of the event but s/he determines that PRISTIQ® did not cause the event, this should be clearly documented on the CRF and the NIS AEM Report Form.

9.4. Definitions of Safety Events

9.4.1. Adverse events

Refer to the '7.4.10.1. Definition of adverse events' clause.

9.4.2. Serious adverse events

Refer to the '7.4.10.2. Definition of serious adverse events (SAEs)' clause.

9.4.3. Scenarios necessitating reporting to Pfizer Safety within 24 hours

Scenarios involving exposure during pregnancy, exposure during breastfeeding, medication error, overdose, misuse, extravasation, lack of efficacy, and occupational exposure are described below.

Exposure during pregnancy

An exposure during pregnancy (EDP) occurs if:

1. A female becomes, or is found to be, pregnant either while receiving or having been exposed to (e.g., environmental) PRISTIQ®, or the female becomes, or is found to be, pregnant after discontinuing and/or being exposed to PRISTIQ® (maternal exposure).

An example of environmental exposure would be a case involving direct contact with a Pfizer product in a pregnant woman (e.g., a nurse reports that she is pregnant and has been exposed to chemotherapeutic products).

2. A male has been exposed, either due to treatment or environmental exposure to PRISTIQ® prior to or around the time of conception and/or is exposed during the partner pregnancy (paternal exposure).

As a general rule, prospective and retrospective exposures during pregnancy reports from any source are reportable irrespective of the presence of an associated AE and the procedures for SAE reporting should be followed.

If a study participant or study participant's partner becomes, or is found to be, pregnant during the study participant's treatment with PRISTIQ®, this information must be submitted to Pfizer, irrespective of whether an adverse event has occurred using the NIS AEM Report Form and the EDP Supplemental Form.

In addition, the information regarding environmental exposure to PRISTIQ® in a pregnant woman (e.g., a subject reports that she is pregnant and has been exposed to a cytotoxic product by inhalation or spillage) must be submitted using the NIS AEM Report Form and the EDP supplemental form. This must be done irrespective of whether an AE has occurred.

Information submitted should include the anticipated date of delivery (see below for information related to termination of pregnancy).

Follow-up is conducted to obtain general information on the pregnancy; in addition, follow-up is conducted to obtain information on EDP outcome for all EDP reports with pregnancy outcome unknown. A pregnancy is followed until completion or until pregnancy termination (e.g., induced abortion) and Pfizer is notified of the outcome. This information is provided as a follow up to the initial EDP report. In the case of a live birth, the structural integrity of the neonate can be assessed at the time of birth. In the event of a termination, the reason(s) for termination should be specified and, if clinically possible, the structural integrity of the

terminated fetus should be assessed by gross visual inspection (unless pre-procedure test findings are conclusive for a congenital anomaly and the findings are reported).

If the outcome of the pregnancy meets the criteria for an SAE (e.g., ectopic pregnancy, spontaneous abortion, intrauterine fetal demise, neonatal death, or congenital anomaly [in a live born, a terminated fetus, an intrauterine fetal demise, or a neonatal death]), the procedures for reporting SAEs should be followed.

Additional information about pregnancy outcomes that are reported as SAEs follows:

- Spontaneous abortion includes miscarriage and missed abortion;
- Neonatal deaths that occur within 1 month of birth should be reported, without regard to causality, as SAEs. In addition, infant deaths after 1 month should be reported as SAEs when the investigator assesses the infant death as related or possibly related to exposure to investigational product

Additional information regarding the exposure during pregnancy may be requested. Further follow-up of birth outcomes will be handled on a case-by-case basis (e.g., follow-up on preterm infants to identify developmental delays).

In the case of paternal exposure, the study participant will be provided with the Pregnant Partner Release of Information Form to deliver to his partner. It must be documented that the study participant was given this letter to provide to his partner.

Exposure during breastfeeding

Scenarios of exposure during breastfeeding must be reported, irrespective of the presence of an associated AE. An exposure during breastfeeding report is not created when a Pfizer drug specifically approved for use in breastfeeding women (e.g., vitamins) is administered in accord with authorized use. However, if the infant experiences an AE associated with such a drug's administration, the AE is reported together with the exposure during breastfeeding.

Medication error

A medication error is any unintentional error in the prescribing, dispensing or administration of a medicinal product that may cause or lead to inappropriate medication use or patient harm while in the control of the health care professional, patient, or consumer. Such events may be related to professional practice, health care products, procedures, and systems including: prescribing; order communication; product labeling, packaging, and nomenclature; compounding; dispensing; distribution; administration; education; monitoring; and use.

Medication errors include:

- Near misses, involving or not involving a patient directly (e.g., inadvertent/erroneous administration, which is the accidental use of a product outside of labeling or prescription on the part of the healthcare provider or the patient/consumer);

- Confusion with regard to invented name (e.g., trade name, brand name).

The investigator must submit the following medication errors to Pfizer, irrespective of the presence of an associated AE/SAE:

- Medication errors involving patient exposure to the product, whether or not the medication error is accompanied by an AE.
- Medication errors that do not involve a patient directly (e.g., potential medication errors or near misses). When a medication error does not involve patient exposure to the product the following minimum criteria constitute a medication error report:
 - An identifiable reporter;
 - A suspect product;
 - The event medication error.

Overdose, Misuse, Extravasation

Reports of overdose, misuse, and extravasation associated with the use of a Pfizer product are reported to Pfizer by the investigator, irrespective of the presence of an associated AE/SAE.

Lack of Efficacy

Lack of efficacy is defined as the failure of expected pharmacologic action or therapeutic benefit.

Reports of lack of efficacy to a Pfizer product are reported to Pfizer by the investigator, irrespective of the presence of an associated AE/SAE or the indication for use of the Pfizer product.

Occupational Exposure

Reports of occupational exposure to a Pfizer product are reported to Pfizer by the investigator, irrespective of the presence of an associated AE/SAE.

Based on the “Safety Information Management Regulations for Drugs, Etc.”, the staff in charge of safety information at Pfizer Korea reports to the Director of Korea Institute of Drug Safety and Risk Management via website, telephone, fax, mail or in the form of electronic document using Appendix Form no. 1 in the Safety Information Management Regulations for Drugs, Etc. (MFDS Notification) within 15 days of awareness or being notified of the serious adverse event/adverse drug reaction in accordance with Article 5 Paragraph 4 of the Re-examination Guideline of New Drugs, Etc (MFDS Notification no. 2015-79). Therefore, in case of a serious adverse event/adverse drug reaction, the investigator immediately notifies the staff in charge of safety information at Pfizer Korea. The investigator completes the

‘Non-Interventional Study Adverse Event Report Form’ and must fax it within 24 hours of awareness of the applicable serious adverse event/adverse drug reaction.

9.5. Single Reference Safety Document

The local product document will serve as the SRSD during the course of the study, which will be used by Pfizer to assess any safety events reported to Pfizer Safety by the investigator during the course of this study.

The SRSD should be used by the investigator for prescribing purposes and guidance.

10. PLANS FOR DISSEMINATING AND COMMUNICATING STUDY RESULTS

For the first 2 years, 6-month reports will be submitted to MFDS (i.e., reports 1-1, 1-2, 2-1, and 2-2). Thereafter, data collected in the 3rd, 4th, and 5th year will be reported to MFDS annually. Final study report (i.e., re-examination report) will be submitted to MFDS in the 6th year to include all data collected during the whole study period (see [Section 4](#)).

11. COMMUNICATION OF ISSUES

In the event of any prohibition or restriction imposed (e.g., clinical hold) by an applicable Competent Authority in any area of the world, or if the investigator is aware of any new information which might influence the evaluation of the benefits and risks of a Pfizer product, Pfizer should be informed immediately.

In addition, the investigator will inform Pfizer immediately of any urgent safety measures taken by the investigator to protect the study patients against any immediate hazard, and of any serious breaches of this NIS protocol that the investigator becomes aware of.

12. PUBLICATION OF STUDY RESULTS

Pfizer fulfils its commitment to publicly disclose study results through posting the results of this study on www.clinicaltrials.gov. Pfizer posts the results of all studies that it has registered on ClinicalTrials.gov regardless of the reason for registration.

The results are posted in a tabular format called Basic Results.

- Basic Results are due within one anniversary year of the PCD and/or LSLV.
- When PCD and LSLV are not the same date, Basic Results are posted one anniversary year from the PCD and the record is updated one anniversary year from the LSLV. The PCD cannot occur after the LSLV.

1 AMENDMENTS FROM PREVIOUS VERSION(S)

Version	Date of Revision	Reason for change	Author name
Version 1.0	11-MAY-2016	1st Version	PPD
Version 2.0	10-JUL-2016	
 1) Deletion duplicated exclusion criteria in Safety Analysis Set 
 • The contents of “Subjects who didn’t receive PRISTIQ®” are included in “Subjects who violated inclusion/exclusion criteria) item 2) Addition the exclusion criteria in Long-term Effectiveness Analysis Set 
 • Addition “Subjects whose each drug-free period is greater than 14 days” item 3) Modification for analysis method and category 
 • Pregnancy • Breast-feeding • Severity of disease • Mean daily dose of PRISTIQ® 4) Modification of calculation method 
 • “Total administration period of PRISTIQ®” 5) Addition the analysis 
 • Other Analyses (Blood Pressure) 	PPD
Version 3.0	15-NOV-2018	
 1) Modification of calculation of Total administration period of PRISTIQ® according to analysis set 2) Clarification the definition of subjects excluded from safety analysis set 3) Addition items of Basic Results Tables 	PPD
Version 4.0	08-NOV-2019	
 1) Exclusion of subjects who are assessed on the final effectiveness evaluation before 8 weeks treatment with PRISTIQ® from the Effectiveness Analysis Set (Section 5.2) 2) Clarification on the derivation of the mean daily dose of PRISTIQ® excluding days of missed doses (Sections 8.2.1.1) 3) Addition of categories for the Total administration period of PRISTIQ®: <12 weeks, ≥12 weeks (Sections 8.2.1.1 and 8.2.1.3) 4) Addition of AE Listings (Section 8.2.1.4) 5) Addition the analysis 	PPD

		
 AE analysis according to the frequency categories of adverse events in the approved local label (Section 8.2.1.4) 
6) Clarification that the effectiveness analyses will be conducted for the periods after 8 weeks and after 6 months of treatment with PRISTIQ® (Section 8.2.2)
	
--	--	---	--

2 INTRODUCTION

Note: In this document any text taken directly from the protocol is *italicized*.

The objective of the Re-examination system in Korea is to re-confirm the clinical usefulness of the product through collecting, reviewing, identifying and verifying the safety and effectiveness information about the product in general practice (usually for a period of 6 years after the product is registered).

PRISTIQ® (desvenlafaxine) is classified as a dual acting Serotonin and Norepinephrine Reuptake Inhibitor (SNRI). Desvenlafaxine extended-release tablets are indicated for the treatment of major depressive disorder (MDD) in adults and for the treatment of moderate to severe vasomotor symptoms (VMS) associated with menopause.

PRISTIQ® was approved by Ministry of Food and Drug Safety (MFDS) in Korea on 06 Feb 2014 for the treatment of Major Depressive Disorder (MDD). This surveillance is conducted for preparing application material for re-examination under the Pharmaceutical Affairs Laws and its Enforcement Regulation, and observation of safety and effectiveness of PRISTIQ® in usual practice according to the Re-examination Guideline of New Drugs, Etc.

The re-exam period for PRISTIQ® is from 06 February 2014 to 05 February 2020, and the final study report should be submitted by 05 May 2020. The analyzed study report based on collected data of 6 years must be submitted to MFDS within 3 months after the end of specified re-examination period (from the product approval date to 6 years afterwards).

2.1 STUDY DESIGN

This study is open-label, non-comparative, observational, non-interventional, prospective and multi-center study in which subjects are administered PRISTIQ® as part of routine practice at Korean health care centers by accredited psychiatrists. The observation period for each subject is from initiating administration of PRISTIQ® until week 8. If administration is discontinued before week 8, observation should be done for at least 28 days from the last administration day. There will be no visit or activity mandated by this study and routine observation will be done during the above-mentioned period.

Study population

600 patients will be enrolled in approximately 20 study centers in this study based on the MFDS re-examination regulation (Section 7.3.3). Most of the study centers would be general hospitals or psychiatric hospitals which have the accredited psychiatrists eligible for conducting PMS study.

Subjects will be enrolled by continuous registration method. It means that the physician should consecutively enroll all patients who are administered PRISTIQ® for the first time and satisfy the inclusion and exclusion criteria after contract is made and the study is initiated.

[Inclusion criteria]

- Adults 19 years of age or older, who have been administered at least one dose of PRISTIQ® for the treatment of Major depressive disorder (MDD).*
- Patients who have been administered PRISTIQ® for the first time after signing the data privacy statement.*

[Exclusion criteria]

Patients to whom PRISTIQ® is contraindicated as per the local labeling;

- Hypersensitivity to desvenlafaxine succinate, venlafaxine hydrochloride or to any excipients in the PRISTIQ® formulation.*
- This drug must not be used in combination with a MAOI, or within at least 14 days of discontinuing treatment with a MAOI.*

2.2 STUDY OBJECTIVES

The objectives of this study are to determine any problems or questions associated with PRISTIQ® after marketing, with regard to the following clauses under conditions of general clinical practice, in compliance with the regulation “Re-examination Guideline of New Drugs, Etc” (Ministry of Food and Drug Safety Notification 2015-79, 2015.10.30, amended).

- Serious adverse event/adverse drug reaction*
- Unexpected adverse event/adverse drug reaction that has not been reflected in the approved drug label.*
- Known adverse drug reaction*
- Non-serious adverse drug reaction*
- Other safety and effectiveness information*

3 INTERIM AND FINAL ANALYSES

This Statistical Analysis Plan (SAP) details the analyses and outputs to be produced for the interim and final analyses.

Note: For the first 2 years, 6-month reports will be submitted to MFDS (i.e., reports 1-1, 1-2, 2-1, and 2-2). Thereafter, data collected in the 3rd, 4th, and 5th year will be reported to MFDS annually. Final study report (i.e., re-examination report) will be submitted to MFDS in the 6th year to include all data collected during the whole study period.

All analyses outlined in this SAP, except for those described below, will be performed for each interim analysis for the periodic report annually.

- Type of medical history
- Type of concomitant medications
- Blood Pressure(SBP, DBP)
- Basic Results Tables

4 HYPOTHESES AND DECISION RULES

Not Applicable

5 ANALYSIS SETS/ POPULATIONS

All subjects entered into this study will be evaluated as to whether they are eligible to be in the Safety Analysis Set and the Effectiveness Analysis Set.

All subjects excluded from the Safety Analysis Set will be accounted for as part of the subject accounting in the Clinical Study Report. Any adverse events reported for subjects excluded from the Safety Analysis Set will also be described.

5.1 SAFETY ANALYSIS SET

Subject who have been administered PRISTIQ® at least once and completed follow up will be included in the safety analysis set.

The following exclusions from the Safety Analysis Set are to ensure that the subjects who are not providing data to the analyses but have some record of treatment do not over-inflate the denominator for the analyses.

The following cases are excluded from the safety analysis set:

- Subjects who were enrolled in the study prior to the site initiating contract date

- Follow-up failure: Subjects for whom adverse event status (Adverse Events status is unknown or missing in the CRF) could not be established
- Subjects who violated inclusion/exclusion criteria (see section 2.1)
- Subjects who did not follow dosage and administration indicated in the local product document

To exclude subjects who have ever taken more than 200mg/day

Statistical analysis on safety parameters will be performed on the safety analysis set.

5.2 EFFECTIVENESS ANALYSIS SET

Subject who have been administered PRISTIQ® at least once and evaluated upon its related effectiveness endpoints at least once will be included in the effectiveness analysis set. The effectiveness analysis set is a subset of the safety analysis set.

The following cases are excluded from the effectiveness analysis set:

- Subjects excluded from safety analysis set listed in section 5.1
- Subjects who are assessed as “Unevaluable” on the final effectiveness evaluation on the CRF
- Subjects who administrated PRISTIQ® less than 8 weeks
- Subjects who are assessed on the final effectiveness evaluation before 8 weeks treatment of PRISTIQ®

Statistical analysis on effectiveness parameters will be performed on the effectiveness analysis set.

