5. RATIONALE AND BACKGROUND

The objective of the Re-examination system in Korea is to re-confirm the clinical usefulness of the product through collecting, reviewing, identifying and verifying the safety and effectiveness information about the product in general practice (usually for a period of 6 years after the product is registered).

PRISTIQ® (desvenlafaxine) is classified as a dual acting Serotonin and Norepinephrine Reuptake Inhibitor (SNRI). Desvenlafaxine extended-release tablets are indicated for the treatment of major depressive disorder (MDD) in adults and for the treatment of moderate to severe vasomotor symptoms (VMS) associated with menopause.

PRISTIQ® was approved by Ministry of Food and Drug Safety (MFDS) in Korea on 06 Feb 2014 for the treatment of Major Depressive Disorder (MDD). This surveillance is conducted for preparing application material for re-examination under the Pharmaceutical Affairs Laws and its Enforcement Regulation, and observation of safety and effectiveness of PRISTIQ® in usual practice according to the Re-examination Guideline of New Drugs, Etc.

The re-exam period for PRISTIQ® is from 06 February 2014 to 05 February 2020, and the final study report should be submitted by 05 May 2020. The analyzed study report based on collected data of 6 years must be submitted to MFDS within 3 months after the end of specified re-examination period (from the product approval date to 6 years afterwards).

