7.4.9.2. Final effectiveness evaluation

Final effectiveness will be evaluated at completing the administration of PRISTIQ® or at around 8 weeks treatment if PRISTIQ® has been still administered. In case of long-term use study subject, the result will be assessed after 6 months treatment of PRISTIQ®. Final effectiveness will be evaluated as ‘improved’, ‘no change’, ‘worse’ or ‘unevaluable’ based on overall patient’s clinical response, CGI-I scale and investigator’s judgment.

- Improved: In the case of judgment that there is the improvement of symptoms related to MDD.
- No change: In the case that there is no significant change compared to patient’s status before PRISTIQ® administration.
- Worse: In the case that symptoms are getting worse compared to patient’s status before PRISTIQ® administration.
- Unevaluable: In the case that the medical charts do not have adequate progress notes to make a judgment on clinical response.

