7.7. Data Analysis

The data collected in this study will be documented in a Statistical Analysis Plan, which will be maintained by the sponsor. This document may modify the plans outlined in the protocol; however, any major modifications of primary endpoint definitions or their analyses will be reflected in a protocol amendment.

No formal sample size calculations were performed for this study. Six hundred (600 patients) or more will be collected as per the requirement by MFDS. Safety summaries will be based on the safety analysis set defined as those patients who met inclusion / exclusion criteria and completed safety follow-up. Effectiveness summaries will be based on the effectiveness analysis set, defined as those patients who took at least 8 weeks of PRISTIQ® and completed effectiveness evaluation.

In addition, special subject groups -elderly group (more than or equal to 65 years old), hepatic disorder group, renal disorder group and pregnancy group- will be analyzed separately.

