6.2 EFFECTIVENESS ENDPOINT(S)

- *[Final effectiveness evaluation]*

Final effectiveness will be evaluated at completing the administration of PRISTIQ® or at around 8 weeks treatment if PRISTIQ® has been still administered. In case of long-term use study subject, the result will be assessed after 6 months treatment of PRISTIQ®. Final effectiveness will be evaluated as 'improved', 'no change', 'worse' or 'unevaluable' based on overall patient's clinical response, CGI-I scale and investigator's judgment.

- Improved: In the case of judgment that there is the improvement of symptoms related to MDD.
- No change: In the case that there is no significant change compared to patient's status before PRISTIQ® administration.
- Worse: In the case that symptoms are getting worse compared to patient's status before PRISTIQ® administration.
- Unevaluable: In the case that the medical charts do not have adequate progress notes to make a judgment on clinical response.

- *[CGI-I scale (Clinical Global Impression – Improvement scale)]*

Clinical effectiveness will be evaluated after 8 weeks treatment (within 2 weeks of the last administration) using CGI-I scale as follows. In case of long-term use study subject, the result will be also assessed after 6 months treatment of PRISTIQ® (within 2 weeks of the last administration).

- 1. Very much improved
- 2. Much improved
- 3. Minimally improved
- 4. No change
- 5. Minimally worse
- 6. Much worse
- 7. Very much worse

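### The improvement rate describes only patients treated and rated at 8 weeks or later; evaluable final ratings from early stoppers enter no effectiveness result and are not counted

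*SAP*

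**What the plan says.** **When the rating is made.** Protocol 7.4.9.2: "Final effectiveness will be evaluated at completing the administration of PRISTIQ® or at around 8 weeks treatment if PRISTIQ® has been still administered". SAP 6.2 repeats this. A patient who stops in week 3 is thus due a final rating at that point, and a continuing patient is rated "at around 8 weeks treatment if PRISTIQ® has been still administered".

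**Who is analysed.** Protocol 7.7 defines the effectiveness set as "those patients who took at least 8 weeks of PRISTIQ® and completed effectiveness evaluation". SAP 5.2 opens more widely: a subject dosed at least once and "evaluated upon its related effectiveness endpoints at least once will be included in the effectiveness analysis set". Its exclusion list then narrows the set again. It removes "Subjects who administrated PRISTIQ® less than 8 weeks" and "Subjects who are assessed on the final effectiveness evaluation before 8 weeks treatment of PRISTIQ", with no window around 8 weeks.

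**What is reported.** SAP 8.2.2 runs the 8-week results on this set: the overall improvement rate with its 95% CI, the final-effectiveness frequencies, the improvement rate by the SAP 8.2.1.3 factors, and the CGI-I distribution. The Basic Results effectiveness table (SAP 8.2.3) uses the same set, and the long-term set (SAP 5.3) is a subset of it.

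**What is counted.** SAP 5 promises an accounting of subjects excluded from the safety set. It promises none for exclusions from the effectiveness set. The flow chart in SAP 8.2.3 gives only the numbers who started and who completed.

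**The concern.** Protocol section 5 gives the purpose as "observation of safety and effectiveness of PRISTIQ® in usual practice". In usual practice some patients stop early. The reasons offered on the CRF for a change in dosing (protocol 7.4.5) include cure or improvement, an adverse event, and withdrawal for lack of efficacy. All three are plausibly related to the outcome. A rate computed only in those who persisted to 8 weeks answers a narrower question than the purpose suggests, and its confidence interval reflects sampling error only, not the selection.

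The plan asks for ratings from early stoppers and then uses them nowhere. Without those ratings, or a count of the exclusions by reason, a reader of the final report cannot tell whether persistence matters to the result.

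**Working it through.** There is no figure in the plan to reproduce. The 600 patients are a regulatory requirement without a sample size calculation (protocol 7.7), and SAP section 4 has no hypotheses.

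**1. Do the excluded ratings return anywhere?** The 8-week results, the Basic Results table and the long-term set all rest on the effectiveness set or a subset of it. SAP section 7 plans no missing-data method. Lack of efficacy is recorded as a safety event (protocol 9.1), so some early failures are visible there, but in no improvement rate. The number treated under 8 weeks can be read from the safety-set exposure table, and the total excluded from the two set sizes. The split by exclusion rule, by reason for stopping or by rating is not planned.

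**2. How large could the difference be?** Let d be the fraction of rated patients who are excluded, and p_ret and p_exc the improvement rates in retained and excluded patients.

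Rate in all rated patients = (1 - d) × p_ret + d × p_exc, so

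difference = p_ret - rate in all rated patients = d × (p_ret - p_exc).

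The documents give none of the three inputs. Assumed ranges: d 10% to 40%, p_ret 60% to 90%, p_exc 20% to 100%. Difference in percentage points:

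| d | p_ret | p_exc 20% | 50% | 80% | 100% |
|---|---|---|---|---|---|
| 10% | 60% | 4.0 | 1.0 | -2.0 | -4.0 |
| 10% | 80% | 6.0 | 3.0 | 0.0 | -2.0 |
| 10% | 90% | 7.0 | 4.0 | 1.0 | -1.0 |
| 25% | 60% | 10.0 | 2.5 | -5.0 | -10.0 |
| 25% | 80% | 15.0 | 7.5 | 0.0 | -5.0 |
| 25% | 90% | 17.5 | 10.0 | 2.5 | -2.5 |
| 40% | 60% | 16.0 | 4.0 | -8.0 | -16.0 |
| 40% | 80% | 24.0 | 12.0 | 0.0 | -8.0 |
| 40% | 90% | 28.0 | 16.0 | 4.0 | -4.0 |

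The extremes are 0.40 × (0.90 - 0.20) = +28 points and 0.40 × (0.60 - 1.00) = -16 points.

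**3. When does the sign turn?** Suppose a share c of early stoppers stop for cure or improvement and all of them are rated improved, while the rest improve at rate q. The difference is zero at c = (p_ret - q)/(1 - q). With p_ret = 0.8 this is 0.30/0.50 = 60% for q = 0.5 and 0.60/0.80 = 75% for q = 0.2. Above that share the restricted rate understates.

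**4. Scale against the confidence interval.** Assume all 600 are in the safety set and rated, and a gap of 20 points. The difference reaches the half-width when 0.20 × d ≥ 1.96 × sqrt(p_ret(1 - p_ret)/(600(1 - d))). The smallest d is 12.9% at p_ret = 0.9, 17.7% at 0.8 and 22.3% at 0.6.

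- If excluded patients do worse, all three cases are possible: about 13% to 22%.
- If they do better, p_ret = 0.9 would need 110% improved, which is impossible. Only 0.8 and 0.6 remain: about 18% to 22%.

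**5. Exposure bands.** SAP 8.2.2 takes over the factors of 8.2.1.3, including exposure under 4 weeks, 4 to under 8, 8 to under 12, and 12 weeks or more. For the effectiveness set, SAP 8.2.1.1 ends exposure at the last dose or, if earlier, at the rating. SAP 5.2 requires both to be at 8 weeks or later. With 8 weeks taken as 56 days (assumed; the SAP does not convert it), exposure is never below 56 days and the first two bands are always empty. Enumerating all last-dose and rating days from 1 to 200 confirms it: 0, 0, 7,336 and 13,689 admissible pairs in the four bands.

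**The case against.** **The restriction is pre-specified and visible.** Protocol 7.7 requires 8 weeks of treatment, and SAP 8.2.2 presents its result as applying after 8 weeks of treatment. A difference arises only against all rated patients, a target that neither document adopts. This stands, and it is why the main set should not change. It does not explain why ratings that the protocol asks for are left unreported.

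**Dropping ratings made before 8 weeks has support.** Protocol 7.4.9.1 places the CGI-I after 8 weeks of treatment, and the final evaluation draws partly on the CGI-I. The exclusion can be read as applying that rule, even though the wording for the final evaluation would allow a rating slightly before week 8. This half of the point is therefore secondary. It leaves early stoppers untouched, because 7.4.9.2 schedules their rating at completing administration.

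**Usable early ratings may be few.** No visit is mandated (protocol 7.1 and 7.4), the required safety follow-up may be by telephone, and a rating may be recorded as unevaluable. This stands: the number is unknown, and the supplementary rate may not settle the question.

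**Effectiveness is a lesser aim.** It appears in the last of five objectives, in a non-comparative study whose design limits are acknowledged (protocol 7.9). This stands and lowers the severity.

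**A stronger reading on timing.** A reader might infer that the early-rating exclusion was a late, result-driven change, since SAP version 4.0 is dated 08-NOV-2019 and planned data collection ended on 01 Dec 2018. The documents do not support that. For this set, SAP 8.2.1.1 already stops exposure at the rating date, so a continuing patient rated early falls under 8 weeks anyway. Version 4.0 may only make an existing effect explicit.

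**Conclusion.** The point holds as a cheap improvement of minor to moderate severity. On the text alone, no early stopper can enter an improvement rate, whatever rating was made, and exclusions from the effectiveness set are not counted by rule. The overall improvement rate, the only effectiveness rate given an explicit 95% CI in SAP 8.2.2, is conditional on persistence.

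A reader might infer that the rate is overstated. The documents do not establish this. Overstatement needs excluded patients to improve less often than retained ones; if most stop for cure or improvement, the sign reverses. The range of +28 to -16 points and the thresholds of 13% to 22% rest wholly on assumed inputs. They show that the difference could matter, not that it does.

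The two empty exposure bands are certain but minor. SAP 8.2.1.1 allows categories to be altered, two bands remain for comparison, and the adverse-event tables, which use the safety set, can fill all four. This is a table tidy-up.

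**What to change.** Keep the protocol 7.7 set as the main set.

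- **SAP 8.2.2:** add a supplementary, descriptive improvement rate with 95% CI in all safety-set subjects with an evaluable final rating. Give separate rows for (a) stopped before 8 weeks, (b) treatment continued to 8 weeks or beyond but rated before 8 weeks, and (c) treated and rated at 8 weeks or later.
- **SAP 5:** report the number excluded from the effectiveness set by each rule of SAP 5.2 and, where recorded, by reason for stopping.
- **SAP 8.2.2 breakdown:** drop the exposure bands under 4 weeks and 4 to under 8 weeks, or show them only in the supplementary set.

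The cost is some SAP wording, one table and one set of counts, all from data the CRF already asks for. No protocol change is needed: the protocol 7.7 set stays as it is, and protocol 7.7 says of the SAP that "This document may modify the plans outlined in the protocol". The downside is that the added rate mixes ratings at stopping with ratings at 8 weeks, which is why the rows must be shown separately, and that it may be less favourable than the main rate.
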